### 6.3.3 Electrocardiogram

Electrocardiograms will be evaluated at the time points indicated in . Electrocardiogram recordings will be obtained after the subject has been supine and at rest for at least five minutes. ECG results will be evaluated at the investigational site to monitor safety during the trial. The Investigator or designee will review, sign, and date each ECG reading. The Investigator or designee will determine if any abnormal results are of clinical significance. The ECG will be repeated if any results are considered by to be clinically significant.

### 6.3.4 Medical History

Medical history (including CD history) will be collected at Visit 1.

A complete medical history will include evaluation (past or present) of the following:

- General
- Head and neck
- Eyes, ears, nose, throat
- Chest/respiratory
- Heart/cardiovascular
- Gastrointestinal/liver
- Gynaecological/urogenital
- Musculoskeletal/extremities
- Skin
- Neurological/psychiatric
- Endocrine/metabolic
- Haematologic/lymphatic
- Allergies/drug sensitivities
- Past surgeries
- Substance abuse
- Any other diseases or disorders

A detailed history of CD, including date of diagnosis, disease severity, disease duration, disease location, associated complications, hospitalisations and extra-intestinal manifestations will be collected during Screening. The subject's CD drug history will also be recorded.

### 6.4 Immunogenicity

Blood samples will be evaluated for the presence of anti-V565 antibody at the time points indicated in . Samples will be collected, labelled, stored, and shipped as detailed in the Central Laboratory Manual. Samples will be processed by LG(

### 6.5 Pharmacokinetics

The concentration of V565 will be determined in serum, and urine at the time points indicated in . Samples will be collected, labelled, stored, and shipped as detailed in the Central Laboratory Manual. Samples will be processed by

### 6.5.1 Blood

Samples will be obtained for the determination of V565 in serum. The following information will be captured for blood sample collection in each subject's eCRF:

- 1. Subject's study number and initials
- 2. Time and date of first V565 dose administration on Day 1 and time and date of the most recent V565 dose prior to PK sampling on Day 14 and 42.
- 3. Time and date of each blood sample collected for PK analysis
- 4. Time and date of subject's most recent ingestion of food prior to dose administration Samples will be collected, processed, labelled, stored, and shipped as detailed in the Central Laboratory Manual.

### 6.5.2 Urine

Urine samples for analysis of V565 in urine will be collected as follows:

- 1. Prior to administration of the first dose of V565 on Day 1. Date/time of urine collections will be captured in each subject's eCRF.
- 2. Post-dose on Day 1, 4 to 8 hours after the first dose of study drug, prior to leaving the clinic
- 3. During the Day 14 and Day 42 visits, complete urine voids will be collected prior to the subject leaving the clinic. The weight (g) or volume (mL) and pH of the urine void along with the date/time of urine collections will be captured in each subject's eCRF. Date and time of the last dose prior to urine collection will also be captured in the eCRF.

Aliquots of the respective urine sample will be frozen and stored until determination of V565 concentration as outlined in the Central Laboratory Manual.

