In Part 2 (n=10) eight healthy volunteers received multiple doses of V565 (1665 mg three times a day [TID]) and two received placebo TID for 14 days. The objectives were to assess safety and tolerability of multiple doses of V565, and to investigate potential immunogenicity following multiple dosing.

In Part 3 (n=4) otherwise healthy subjects with a terminal ileostomy received a single dose of V565 1665 mg to evaluate V565 luminal concentrations at the terminal ileum.

Part 4 (n=6) was a single ascending dose study that investigated systemic exposure in subjects with mild to moderate CD. Two subjects received a single 555 mg dose and, following review by the Safety Review Committee, a further four subjects received a single 1665 mg dose. This was considered important as patients with CD have increased intestinal permeability compared to healthy volunteers, which could potentially lead to increased systemic exposure. In addition, in this part of the study, urine collections were scheduled as an indirect method of assessing systemic exposure in case V565 was not detectable in serum samples.

The results of the Phase 1 study are summarised below:

- V565 has been administered to 37 human subjects in single doses up to 4995 mg and in multiple doses up to 1665 mg TID for 14 days. V565 was safe and well tolerated. There were no deaths, no serious adverse events (SAEs) and no adverse events (AEs) leading to withdrawal or change of dose. Almost all AEs were mild, with the only severe AE being a report of tonsillitis with initial symptoms starting approximately three hours after a 62 mg dose.
- V565 was not detectable in any serum sample in any part of the study.
- V565 was detected in the urine collection taken four to eight hours after dosing of one subject with CD in Part 4, confirming that active V565 passes across the lamina propria.
- No neutralising anti-drug antibodies were detected in any subject.
- High concentrations of active V565 were detected in ileal fluid and faeces.

Additional non-clinical information is provided in the current version of the V565 Investigator's Brochure (IB).

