#### 4.2.2 Treatment Period

During the treatment period, the subject will attend three site visits (Day 1, Day 14 and Day 42). If possible, site visits will be scheduled for the morning. The window for the Day 14 and Day 42 visits is -3 days to +1 day.

On Day 1, subject compliance with diary completion will be reviewed to confirm that diary compliance is still acceptable. If all eligibility requirements have been met (including those based on the results of the ileocolonoscopy), the subject will be randomised. If not, the subject will be considered a screen failure and the reason for the screen fail will be recorded.

Eligible subjects will be randomly assigned to receive one of two oral regimens: V565 555 mg TID or placebo.

The Day 1 assessments and procedures presented in will be completed prior to starting treatment with study drug. Treatment will begin on Day 1 at the site and continue to Day 42. Additional information on dosing is available in Section 5.8.

Subjects will continue to fill out their diaries daily throughout the treatment period. At each visit, site personnel will review the diaries and assess compliance with study drug administration and with the use of the diary.

Pharmacokinetic samples (blood and urine) will be collected at each study visit. On Day 1, subjects will be asked to provide a pre-treatment sample and an additional sample 4 to 8 hours after the first dose of study drug.

The subjects take their last dose of study drug on Day 42. The subjects will return to the site on Day 42 for the assessments and procedures indicated in . The subject diaries will be collected at this time. Subjects participating in the endoscopy substudy will have their second ileocolonoscopy performed on Day 42.

### 4.2.3 Follow-up: Day 56

The subject will return to the site for a follow-up visit at Day 56, approximately two weeks after the last dose of study drug. The procedures performed during the follow-up visit are presented in .

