# 5.8 Selection and Timing of Dose for Each Subject

Each dose will consist of three capsules of V565 (three 185-mg capsules, total dose 555 mg) or placebo. Study drug will be administered orally TID. The subjects will be instructed to take the capsules with sufficient fluid one hour before meals and at least two hours after the previous meal.

No dose adjustments are permitted.

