### **16.** PHARMACOKINETIC ANALYSIS

Individual PK serum blood sample collection dates/times, and the associated V565 concentrations will be listed by visit for each subject.

The PK urine sample collection dates/times and V565 excreted will be listed by visit for each subject. The amount excreted will be determined as V565 concentration × urine volume of the urine sample at the visit.

Serum and urine V565 concentrations will be summarized using descriptive statistics by visit on the PK population.

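### Urine V565 has a fixed post-dose time on Day 1 but not on Days 14 and 42, and the SAP's by-visit summary ignores time since last dose, so descriptive differences between visits cannot be read as changes in exposure

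*Protocol*

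**What the plan says.** - **Protocol 6.5.2, Day 1.** There are two urine samples. One is pre-dose: "Prior to administration of the first dose of V565 on Day 1". The other is tied to dosing: "Post-dose on Day 1, 4 to 8 hours after the first dose of study drug, prior to leaving the clinic".
- **Protocol 6.5.2, Days 14 and 42.** "During the Day 14 and Day 42 visits, complete urine voids will be collected prior to the subject leaving the clinic". Weight or volume, pH and collection time are recorded, and the section adds: "Date and time of the last dose prior to urine collection will also be captured in the eCRF".
- **Protocol 4.2.2 and 5.8.** On clock time: "If possible, site visits will be scheduled for the morning". On dosing: "Study drug will be administered orally TID". Neither section says whether the visit falls before or after that day's first dose.
- **SAP section 16.** "Serum and urine V565 concentrations will be summarized using descriptive statistics by visit on the PK population". Collection times and the amount excreted (concentration times volume) are listed by visit. Time since last dose is not derived, listed or used for grouping.
- **Protocol synopsis and 8.2.4.** The synopsis has serum and urine results summarised by planned sampling time and treatment group. Section 8.2.4 plans only listings for urine.
- **SAP 6.4.** By-visit summaries of all objectives show Day 42 and Early Termination as one combined visit.

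**The concern.** Urine concentration is a named pharmacokinetic endpoint in the protocol synopsis. Phase 1 collected urine as an indirect measure of exposure in case serum was negative. Serum was negative in every sample, whereas Protocol 2.1 reports: "V565 was detected in the urine collection taken four to eight hours after dosing of one subject with CD in Part 4". Low systemic exposure is also the reason Protocol 2.2 gives for expecting a better safety profile than parenteral anti-TNFα products.

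In Phase 1, repeat dosing was studied in healthy volunteers only, and the six subjects with Crohn's disease had single doses. Within this programme, the urine table is therefore an early view of repeat-dose exposure in patients, and readers will compare Day 1 with Day 42 whether or not a test is planned. If the rows differ in time since dose, that comparison mixes three things: any real change in absorption or elimination, carry-over from earlier doses, and sampling time.

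**Working it through.** The documents state no figure on this point, so there is nothing to reproduce. The check is a comparison of the sections, followed by two illustrations on declared assumptions.

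**1. The rules side by side**

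| Sample | Time since dose set by the protocol | Treatment in SAP 16 |
|---|---|---|
| Day 1 pre-dose | before any dose | by visit |
| Day 1 post-dose | 4 to 8 h after the first dose | by visit |
| Day 14, Day 42 | none; during the visit, morning if possible | by visit |
| Early Termination | none; may be off drug | shown with Day 42 (SAP 6.4) |

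The Day 1 post-dose row has a defined time since dose. The Day 14 and Day 42 rows take whatever time the visit happens to give.

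**2. How far sampling time alone can move the value**

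Assumptions, none from the documents: one compartment, first-order absorption after a lag, urinary excretion rate proportional to the body level, dosing every 8 h, and identical kinetics at all visits. Lag is 1, 2 or 3 h; absorption rate ka is 0.75 or 1.5 per h; half-life is 1, 2 or 4 h. That gives 3 × 2 × 3 = 18 sets.

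- Single dose, for t > lag: C(t) = ka/(ka − ke) × [exp(−ke(t − lag)) − exp(−ka(t − lag))], with ke = ln 2 / half-life.
- Repeated dosing: the sum of C(t + 8k) over k = 0 to 29.
- Ratio: mean under repeated dosing over the sampled window, divided by the mean of C(t) over 4 to 8 h after the first dose.

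| Window sampled on Day 14/42 | Ratio to Day 1, lowest to highest of 18 sets |
|---|---|
| 0 to 2 h | 0.11 to 2.6 |
| 2 to 4 h | 0.54 to 5.0 |
| 4 to 8 h (matched) | 1.00 to 1.44 |

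Nothing real changes between visits in any of these sets. One set shows both directions: with lag 2 h, ka 1.5 per h and half-life 1 h, the ratio is 0.11 for urine from 0 to 2 h and about 3.0 for urine from 2 to 4 h. The 1.00 to 1.44 left after matching is carry-over. With carry-over removed (both windows under repeated dosing), timing alone gives 0.11 to 2.6 for 0 to 2 h against 4 to 8 h, and 0.53 to 4.9 for 2 to 4 h against 4 to 8 h.

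**3. How many later voids might fall in the 4 to 8 h window**

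The documents give no clock times, so these are assumed. Dose and void times are uniform, and the proportion is the area where the gap is 4 to 8 h divided by the total area.

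| Morning dose | Void | Proportion at 4 to 8 h |
|---|---|---|
| 06:00–08:00 | 08:30–12:00 | 2/7 = 0.29 |
| 06:00–08:00 | 08:00–11:00 | 0.5/6 = 0.08 |
| 07:00–09:00 | 09:00–12:00 | 0.5/6 = 0.08 |
| 05:30–07:00 | 09:00–12:00 | 2.625/4.5 = 0.58 |

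If the last dose was the previous evening (20:00–22:00) and the void is at 08:30–12:00, the gap is 10.5 to 16 h and the proportion is 0. On Day 1 it is 1 by design.

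**4. Early Termination**

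The planned numbers are 84 randomised to V565 and 76 completing, so 84 − 76 = 8 subjects could contribute an Early Termination sample to the Day 42 row. Protocol 4.2.5 schedules that visit after the decision to stop study drug.

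**The case against.** The best defence is that no planned inference is touched. The pharmacokinetic objective is only to determine concentrations, and neither document plans a test or estimate of change. Collection time and last-dose time are recorded, so time since dose can be worked out without any design change. Days 14 and 42 share one rule, so between those two visits timing mainly adds noise. All of this stands, and it is why severity is low. It does not remove the mismatch, because SAP 16 as written does not use the recorded dose time.

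Several stronger readings are tempting, and the documents do not support them:

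- **Repeat-dose exposure will be understated.** The direction is unknown; the illustration runs from about one tenth to about five times the Day 1 value.
- **4 to 8 h is the detection window.** This rests on one Phase 1 subject, and the protocol does not report what other urine intervals showed.
- **Urine is the only working measure of systemic exposure.** Serum is sampled too, and serum in repeat-dosed patients with Crohn's disease is not yet known.
- **The two Day 1 samples will be merged.** SAP Appendix 1 has separate Baseline and Day 1 labels, and SAP 6.2 defines baseline as the last value before first dose, so they can be kept apart. SAP 16 simply does not say so.
- **Most later voids miss the window.** The 0 to 58% range depends entirely on assumed clock times. It also counts only the latest dose and treats a void as an instant, although it holds urine formed since the previous void.

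**Conclusion.** The point holds as a limit on interpretation. In the protocol and SAP text, Day 1 post-dose urine has a fixed time since dose, Day 14 and Day 42 urine does not, and SAP 16 summarises by visit without using the recorded last-dose time. Descriptive differences between Day 1 and later visits could therefore reflect sampling time, in either direction, together with carry-over. On the assumed kinetics, sampling in the first four hours after a dose gives 0.11 to 5.0 times the Day 1 value with no true change; matching windows narrows this to 1.00 to 1.44. These are excretion rates, and reading them as concentrations also assumes a steady urine flow.

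Severity is low: a named endpoint is affected, but only in how its descriptive table is read. No efficacy result depends on it. One condition remains. The Schedule of Events table is missing from the text reviewed, and the Central Laboratory Manual is a separate document. Either could set a post-dose time for Days 14 and 42, and both should be checked first.

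**What to change.** After that check, amend SAP section 16:

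1. Show Day 1 pre-dose and Day 1 4 to 8 h urine as separate rows, in line with the synopsis's summary by planned sampling time.
2. Derive time since last dose for every urine sample from the recorded dose and collection times, and list it beside the result.
3. Summarise Day 14 and Day 42 urine by band of time since last dose: under 4 h, 4 to 8 h, over 8 h.
4. Set the Day 1 post-dose row beside only the 4 to 8 h samples of Days 14 and 42, with a note that carry-over from repeated dosing remains.
5. Do not pool Early Termination urine taken off drug with Day 42.

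Every input is already collected, so the change costs a few lines of SAP text and some programming. The price is smaller cells: three bands at each of two visits, some perhaps with few samples, in which case the listing carries most of the information. Collecting Day 14 and Day 42 urine in a set window is an option for the sponsor. It would mean later or longer visits, and the SAP change does not depend on it.

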### 6.6 Pharmacogenetics

A blood sample for exploratory genetic research will be obtained from consenting subjects pre-dose, at Visit 3 (Day 1). Although genotype is a stable parameter, sample collection prior to the first dose on Day 1 is preferred to avoid introducing bias through excluding subjects who may withdraw due to an AE; it is important to include such subjects in any genetic analysis. If the sample is not drawn at Visit 3 (Day 1), it may be taken at any visit until the last study visit. Only one sample should be collected per subject for possible genetic analysis. Samples will be collected, labelled, stored, and shipped as detailed in the Central Laboratory Manual.

Participation in this optional genetic research is voluntary. A separate ICF will be used for subjects who elect to contribute samples for pharmacogenetic analyses. This sample may be

analysed only for genes involved in the drug metabolism, safety, and clinical efficacy of V565. These samples may provide information on how individuals metabolise and react to the study drug.

The processes adopted for the coding and storage of samples for genetic analysis are important to maintain subject confidentiality. Samples will be stored for a maximum of 15 years from the date of the last subject's last visit, after which they will be destroyed. Samples will be stored and used until no further analyses are possible or the maximum storage time has been reached.

For all samples, irrespective of the type of coding used, the DNA will be extracted from the blood sample. The DNA sample will be assigned a unique number replacing the information on the sample tube. Thereafter, the DNA sample will be identifiable by the unique DNA number only. No personal details identifying the individual will be available to any person.

# 6.7 Appropriateness of Measurements

All efficacy, safety, and tolerability assessments used in this study are standard and generally accepted as appropriate for this type of study.

# 7.0 QUALITY CONTROL AND QUALITY ASSURANCE

According to the Guidelines of Good Clinical Practice (CPMP/ICH/135/95), the Sponsor is responsible for study drug documentation and maintaining quality assurance and quality control systems with written Standard Operating Procedures (SOPs).

Quality control will be applied to each stage of data handling.

The following steps will be taken to ensure the accuracy, consistency, completeness, and reliability of the data:

- Investigator meeting(s)
- Central laboratories for clinical laboratory parameters
- Site Initiation visit
- Early site visits post-enrolment
- Routine site monitoring
- Ongoing site communication and training
- Data management quality control checks
- Continuous data acquisition and cleaning
- Internal review of data
- Quality control check of the final clinical study report

In addition, the Sponsor and/or Quintiles Clinical Quality Assurance Department may conduct periodic audits of the study processes, including, but not limited to study site, site visits, central laboratories, vendors, clinical database, and final clinical study report. When audits are conducted, access must be authorised for all study related documents including medical history and concomitant medication documentation to authorised Sponsor's representatives and regulatory authorities.

### 7.1 Monitoring

The Sponsor has engaged the services of a contract research organisation (CRO), to perform all monitoring functions within this clinical study. monitors will work in accordance with SOPs. Monitors will establish and maintain regular contact between the Investigator and the Sponsor.

Monitors will evaluate the competence of each study site, informing the Sponsor about any problems relating to facilities, technical equipment, or medical staff. During the study, monitors will check that written informed consent has been obtained from all subjects correctly and that data are recorded correctly and completely. Monitors are also entitled to compare entries in eCRFs with corresponding source data and to inform the Investigator of any errors or omissions. Monitors will also control adherence to the protocol at the study site.

Monitoring visits will be conducted according to all applicable regulatory requirements and standards. Regular monitoring visits will be made to each site while subjects are enrolled in the study. The monitor will make written reports to the Sponsor on each occasion contact with the Investigator is made, regardless of whether it is by phone or in person.

During monitoring visits, entries in the eCRFs will be compared with the original source documents (source data verification).

# 7.2 Data Management/Coding

Data generated within this clinical study will be handled according to the relevant SOPs of the Data Management and Biostatistics departments of

Electronic Data Capture (EDC) will be used for this study, meaning that all eCRF data will be entered in electronic forms at the study site. Data collection will be completed by authorised study site staff designated by the Investigator. Appropriate training and security measures will be completed with the Investigator and all authorised study site staff prior to the study being initiated and prior to any data being entered into the system for any study subjects.

All data must be entered in English. The eCRFs should always reflect the latest observations on the subjects participating in the study. Therefore, the eCRFs are to be completed as soon as possible during or after the subject's visit. To avoid inter-observer variability, every effort should be made to ensure that the same individual who made the initial baseline determinations completes all efficacy and safety evaluations. The Investigator must verify that all data entries in the eCRFs are accurate and correct. If some assessments are not done, or if certain information is not available or not applicable or unknown, the Investigator should indicate this in the eCRF. The Investigator will be required to sign off electronically on the clinical data.

The monitor will review the eCRFs and evaluate them for completeness and consistency. The eCRF will be compared with the source documents to ensure that there are no discrepancies between critical data. All entries, corrections, and alterations are to be made by the responsible Investigator or his/her designee. The monitor cannot enter data in the eCRFs. Once clinical data of the eCRF have been submitted to the central server, corrections to the data fields will be audit trailed, meaning that the reason for change, the name of the person who performed the change, and the time and date of the change will be logged. Roles and rights of the site staff responsible for entering the clinical data into the eCRF will be determined in advance. If additional corrections are needed, the responsible monitor or Data Manager will raise a query in the EDC application. The appropriate study site staff will answer queries sent to the Investigator. This will be audit trailed by the EDC application, meaning that the name of investigational staff, time and date stamp are captured.

The eCRF is essentially considered a data entry form and should not constitute the original (or source) medical records unless otherwise specified. Source documents are all documents

and sources of information used by the Investigator or hospital that relate to the subject's medical history, that verify the existence of the subject, the inclusion and exclusion criteria and all records covering the subject's participation in the study. They include laboratory notes, ECG results, memoranda, pharmacy dispensing records, subject files, etc.

The Investigator is responsible for maintaining source documents. These will be made available for inspection by the study monitor at each monitoring visit. The Investigator must submit a completed eCRF for each subject who receives study drug, regardless of duration. All supportive documentation submitted with the eCRF, such as laboratory or hospital records, should be clearly identified with the study and subject number. Any personal information, including subject name, should be removed or rendered illegible to preserve individual confidentiality.

eCRF records will be automatically appended with the identification of the creator by means of their unique UserID. Specified records will be electronically signed by the Investigator to document his/her review of the data and acknowledgement that the data are accurate. This will be facilitated by means of the Investigator's unique UserID and password; date and time stamps will be added automatically at time of electronic signature. If an entry on an eCRF requires change, the correction should be made in accordance with the relevant software procedures. All changes will be fully recorded in a protected audit trail, and a reason for the change will be required.

Adverse events will be coded using the Medical Dictionary for Regulatory Activities (MedDRA). Concomitant medications will be coded using the World Health Organization (WHO) Drug Dictionary and Anatomical Therapeutic Chemical (ATC) system. Concomitant diseases/medical history will be coded using MedDRA.

